- ⁹ In addition to study visits outlined in the SOA, participants will be asked to complete twice weekly voice recordings at home.
- ¹⁰ Drug will only be dispensed at this visit if the participant continues in the OLE.
- ¹¹ Participants will only have a Follow-Up Safety Call at this time if they *do not* continue on in the OLE. Participants who continue into OLE will have a Follow-Up Safety Call after their last dose of IP during the OLE period.
- ¹² Vital status, defined as a determination of date of death or death equivalent or date last known alive, will be determined for each randomized participant at the end of the placebo-controlled portion of their follow-up (generally the Week 24 Visit, as indicated). If at that time the participant is alive, his or her vital status should be determined again at the time of the last participant's last visit (LPLV) of the placebo-controlled portion of a given regimen. We may also ascertain vital status at later time points by using publicly available data sources as described in section 8.15 of the Master Protocol.
- ¹³ If the CSF collection is unable to be performed for logistical reasons, such as scheduling, at the Week 16 Visit, it may be performed at the Week 24 Visit.
- ¹⁴ If a participant's visit occurs in the morning, the participant should be instructed that the morning dose of study medication should not be taken, and the morning dose should be administered in-clinic 1-2 hours prior to the **POST-DOSE** ECG. If a participant's visit occurs in the afternoon, the participant should be instructed to take the morning dose immediately upon waking in the morning, and the second dose should be administered in-clinic 1-2 hours prior to the **POST-DOSE** ECG.
- ¹⁵ At the regimen-specific Screening visit (and Week 24 for participants enrolling in OLE), QTcF will be determined by the mean of three, 10-second recordings of a 12-Lead ECG (performed at least 1 minute a part) **BEFORE** IP administration. For participants on Nuedexta, the Nuedexta dose should be taken within 6 hours **BEFORE** the ECG, refer to the MOP for additional guidelines.
- ¹⁶ At Baseline and Week 4 (and Week 24 for participants enrolling in OLE) QTcF will be determined by a single 10-second 12-lead ECG, 1-2 hours **AFTER** IP administration. If stopping or monitoring rules are met, refer to Section 4.4. For participants on Nuedexta, the Nuedexta dose should be taken within 6 hours **BEFORE** the ECG, refer to the MOP for additional guidelines.

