Clinical Safety Labs ^{2,12}	Master		X	X		X		X	
Biomarker Blood Collection ¹²	Master					X		X ⁹	
Biomarker Urine Collection	Master					X		X ⁹	
Concomitant Medication Review	Master	X	X	X	X	X	X	X	
Adverse Event Review ³	Master	X	X	X	X	X	X	X	X
Columbia-Suicide Severity Rating Scale	Master		X	X		X		X	
Administer/Dispense	Master		X ¹⁰	X		X		X ¹⁴	

Investigational Product (IP)									
Drug Accountability/ Compliance	Master	X ¹⁶	X	X	X ¹⁶	X	X ¹⁶	X	

¹ Vital signs include weight, systolic and diastolic pressure, respiratory rate, heart rate and temperature. Height in cm measured at Master Protocol Screening Visit only.

² Clinical safety labs include hematology (CBC with differential), complete chemistry panel, thyroid function and urinalysis. Serum pregnancy testing will occur in women of child-bearing potential at the Master Protocol Screening Visit and as necessary during the study. Pregnancy testing is only repeated as applicable if there is a concern for pregnancy.

³ Adverse events that occur after signing the master protocol consent form will be recorded.

⁴ Participants who continue into the OLE will have a Follow-Up Safety Call (as described in the body of this RSA) after their last dose of IP during the OLE period.

⁵ The duration of the OLE will be at least 24 weeks.

⁶ Participants who continue into the OLE and early terminate will be asked to complete an Early Termination Visit and Follow-Up Safety Call as described in Section 6.1.10..

⁷ If a participant's visit occurs in the morning, the participant should be instructed that the morning dose of study medication should not be taken, and the morning dose should be administered in-clinic 1-2 hours prior to the **POST-DOSE** ECG. If a participant's visit occurs in the afternoon, the participant should be instructed to take the morning dose immediately upon waking in the morning, and the second dose should be administered in-clinic 1-2 hours prior to the **POST-DOSE** ECG.

⁸ QTcF will be determined by a single 10-second 12-lead ECG 1-2 hours **AFTER** IP administration. If stopping or monitoring rules are met refer to Section 4.4. For participants on Nuedexta, the Nuedexta dose should be taken within 6 hours **BEFORE** the ECG, refer to the MOP for additional guidelines.

⁹ Biomarker Blood Collection, Biomarker Urine Collection and all regimen-specific samples will occur at OLE Weeks 24 and 52 only.

¹⁰ IP must be administered at 1-2 hours prior to the **POST-DOSE** ECG.

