- QTcF will be measured by a mean of 3 (triplicate) 12-lead ECG assessments
 - Three 10-second ECG recordings should be performed, with at least one minute between each recording. QTcF will be automatically calculated by the ECG machine, and will be copied onto source documents. Mean QTcF from the three ECG recordings will be calculated manually. The SI should review and confirm the mean QTcF value.
- If the mean QTcF is >450 ms for men and >470 ms for women, then participant will screen fail and will not be randomized within the regimen.
- For participants on Nuedexta, the Nuedexta dose should be taken within 6 hours before triplicate ECG.

[figure not shown]
[figure not shown]

Figure 3: ECG Monitoring Flow for Regimen Specific Baseline post-dose and Week 4 post-dose Visits*

*For participants on Nuedexta, the Nuedexta dose should be taken within 6 hours before the ECG

QTcF value will be automatically calculated by the ECG machine, and will be copied into source documents (Figure 3):

- QTcF will be measured by a single 12-lead ECG, 1-2 hours post-dose administration.
- If QTcF meets Stopping/Monitoring Rules, then ECG will be repeated twice¹ and the QTcF will be determined by the average of the 3 ECGs.
- If the average QTcF meets Stopping Rules, IP will be held, and a follow-up ECG will be performed as soon as practicable (but at least 2 days after stopping IP) to ensure recovery from QT-prolongation.
- If the average QTcF meets Monitoring Rule for the 1st time, participant will be instructed to continue on IP per-protocol and have a follow up, post-dose ECG after 3-14 days
- If a participant meets the Monitoring Rule for the second time, the participant will be instructed to decrease IP to QD dosing for the remainder of the study.
 - A follow-up ECG should occur 3-14 days after decreasing to QD dosing. If the participant meets the monitoring rule for the 3rd time, the participant must discontinue IP immediately.

¹ Standard ECG procedure for abnormal QTcF readings will be for the ECG to be repeated twice (at least 5 minutes after the 1st ECG, and with an interval of at least 1 minute between each of the 2 additional 10-second recordings), and the mean of the 3 measurements will be used to determine final QTcF.

ECG Monitoring Flow at Week 24 for Participants not Enrolling into the OLE

QTcF will be automatically calculated by the ECG machine, and will be copied into source documents:

- QTcF will be measured by **a single** 12-lead **pre-dose** ECG.

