 - For participants taking Nuedexta, the Nuedexta dose should be taken within 6 hours before the ECG
- If QTcF meets Stopping/Monitoring Rules, then ECG will be repeated twice² and the QTcF will be determined by the average of the 3 ECGs.
- If the average QTcF meets Stopping Rules, IP will be stopped, and a follow-up ECG will be performed as soon as practicable (but at least 2 days after stopping IP) to ensure recovery from QT-prolongation.

ECG Monitoring Flow at Week 24 for Participants who choose to Enroll into the OLE

- Baseline QTcF for the purpose of OLE will be measured by **a mean of 3 (triplicate)** 12-lead **pre-dose** ECG assessments
 - Three 10-second ECG recordings should be performed, with at least one minute in between each ECG recording. QTcF will be automatically calculated by the ECG machine, and will be copied onto source documents. Mean QTcF from the three ECG recordings will be calculated manually and used as Baseline pre-dose QTcF for the OLE. The SI should review and confirm the mean QTcF.
- For participants taking Nuedexta, the Nuedexta dose should be taken within 6 hours before the ECG.
- If the mean QTcF is >450 ms for men and >470 ms for women at the Week 24 Visit, then participant will not be eligible to continue into the OLE.
- The OLE IP should then be administered to the participant, and **a single** 10-second ECG should be collected 1-2 hours after administration of the OLE IP.
- If QTcF meets Stopping/Monitoring Rules then ECG will be repeated twice² and the QTcF will be determined by the average of the 3 ECGs.
- If the mean QTcF meets Stopping Rules, IP will be held , and a follow-up ECG will be performed as soon as practicable (but at least 2 days after stopping IP) to ensure recovery from QT-prolongation.
- If the mean QTcF meets Monitoring Rule, participant may continue on IP per-protocol and have another ECG after 3 -14 days.
- If a participant meets the Monitoring Rule for the second time, the participant may decrease to QD dosing for the remainder of the study.
- A follow-up ECG should occur 3-14 days after decreasing to QD dosing. If the participant meets the monitoring rule during this follow-up ECG, the participant must discontinue IP immediately.

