5.7 Dosage Changes

After the 2-week up-titration period, participants who are unable to tolerate a BID schedule will be allowed to stay in the study at the lower dose QD schedule for 1 additional week. After 1 additional week of study intervention on the QD schedule, the dose will be increased to a BID dose schedule. If the participant cannot tolerate the second increase to a BID dose schedule, they will be allowed to continue on QD for the remainder of the study.

If a participant meets the ECG Monitoring Rule for a second time, the participant may decrease to QD dosing for the remainder of the study, as long as the Monitoring Rule is not met for a third time.

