6.2.2 Week 4 OLE Visit

If a participant's visit occurs in the morning, the participant should be instructed not to take the morning dose at home, and the morning dose should be administered in-clinic 1-2 hours prior to the post-dose ECG. If a participant's visit occurs in the afternoon, the participant should be instructed to take the morning dose immediately upon waking in the morning, and the second dose should be administered in-clinic 1-2 hours prior to the post-dose ECG.

This visit will take place in-person 28 ± 7 days after the Week 24 Visit of the placebo-controlled portion of the trial. The following procedures will be performed:

- Collect vital signs including weight
- Perform SVC
- Collect Home Spirometry
- Administer ALSFRS-R questionnaire
- Administer single ECG 1-2 hours **AFTER** IP is administered
 - Note: if the participant is taking Nuedexta, the Nuedexta dose should be taken within 6 hours prior to the post-dose ECG. If participant has taken Nuedexta outside of this window, the ECG should still be completed and a protocol deviation recorded. Refer to the MOP for additional guidance.
- Collect blood samples for Clinical Safety Labs and, for WOCBP, for pregnancy test if applicable

- All blood samples should be collected after the ECG is performed. If the blood samples cannot be collected after the ECG due to scheduling constraints, blood samples should be collected at least one hour prior to the ECG.
- Review concomitant medications
- Assess and document AEs, including Key Study Events (*see section 10.3 of Master Protocol*)
- Administer the C-SSRS Since Last Visit questionnaire
- Perform investigational product compliance
- Remind participant to bring investigational product to the next visit

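### In the open-label extension (OLE), a second QT Monitoring Rule hit permits reduction to QD but does not clearly require it, and the written discontinuation step depends on that reduction

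*Protocol*

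**What the plan says.** The protocol says three times what follows a second Monitoring Rule hit (QTcF above 480 ms, or a rise above 60 ms from baseline).

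- **Section 4.4, Baseline and Week 4 flow.** At the second hit, "the participant will be instructed to decrease IP to QD dosing for the remainder of the study". It continues: "A follow-up ECG should occur 3-14 days after decreasing to QD dosing. If the participant meets the monitoring rule for the 3rd time", IP must be stopped at once.
- **Section 4.4, Week 24 flow for participants entering the OLE.** "If a participant meets the Monitoring Rule for the second time, the participant may decrease to QD dosing". A follow-up ECG is timed 3-14 days from the reduction, and then: "If the participant meets the monitoring rule during this follow-up ECG, the participant must discontinue IP immediately".
- **Section 5.7, not limited to either period.** If a participant "meets the ECG Monitoring Rule for a second time, the participant may decrease to QD dosing", on condition that the rule is not met a third time.

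The schedule footnotes point back to Section 4.4. Footnote 16 does so for the placebo-controlled period ("If stopping or monitoring rules are met, refer to Section 4.4"), and OLE footnotes 8 and 15 do so for the OLE ECGs ("If stopping or monitoring rules are met refer to Section 4.4"). The OLE visit sections (6.2.1 to 6.2.7) give no dosing instruction after a hit. SAP 2.7 describes QD dosing only for intolerance, and SAP 6.6.3 only counts hits. The SAP's precedence table cannot settle the wording, because all three statements sit in the same regimen appendix.

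**The concern.** QT prolongation is the risk that Section 5.11.1 names for this drug, and the ECG rules are its mitigation. In the OLE everyone receives active drug. A site that kept a participant on BID after two hits would breach no sentence headed for the OLE. It would also never start the clock for the follow-up ECG, because that ECG is timed from the reduction. The written discontinuation step would then have no ECG to act on.

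The Stopping Rules do not fully cover this. They need QTcF above 500 ms, or above 480 ms together with a rise above 60 ms. A participant repeatedly between 481 and 500 ms with a smaller rise meets the Monitoring Rule each time and never the Stopping Rules.

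**Working it through.** **1. The texts side by side**

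| | Baseline/Week 4 flow (4.4) | OLE flow (4.4) | Section 5.7 |
|---|---|---|---|
| Second hit | Instructed to reduce | May reduce | May reduce |
| Follow-up ECG | 3-14 days after reduction | 3-14 days after reduction | Not mentioned |
| Mandatory stop | Third hit | Hit at that follow-up ECG | Third hit implied as the limit of staying on QD |

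One statement of three is directive, and it is headed for the Baseline and Week 4 visits.

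**2. Time to the next scheduled OLE ECG if BID is kept**

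Inputs: for OLE Week 4, "This visit will take place in-person 28 ± 7 days after the Week 24 Visit", so Day 21 to 35 (Section 6.2.2). OLE Week 24 is Day 196 ± 14, so Day 182 to 210 (Section 6.2.7). Dosing is QD for the first two OLE weeks (Section 6.2). I assume hits are counted afresh from OLE entry, which the protocol does not state.

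*First hit at OLE entry, second at OLE Week 4:*
- Nominal: 196 − 28 = 168 days.
- With windows: 182 − 35 = 147 to 210 − 21 = 189 days.

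*First hit at OLE Week 4, second at its 3-14 day repeat (Day 31 to 42):*
- 196 − 42 = 154 to 196 − 31 = 165 days.

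*First hit at OLE entry, second at its 3-14 day repeat (Day 3 to 14, during the QD start):*
- To Week 4, nominal: 28 − 14 = 14 to 28 − 3 = 25 days.
- With the Week 4 window: 21 − 14 = 7 to 35 − 3 = 32 days.
- Of this, BID dosing nominally covers 28 − 14 = 14 days.

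The label Week 24 and Day 196 differ by 196 − 168 = 28 days. If Day 168 is meant, the OLE Week 4 figures become 140 days nominal and 119 to 161 with windows, and the 154-165 range becomes 126-137.

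Most of the long interval is the routine schedule. With a mandatory reduction after a second hit at OLE Week 4, there would be an ECG at 3-14 days and then 168 − 14 = 154 to 168 − 3 = 165 days on QD before the next scheduled ECG. That next ECG is pre-dose, so it is not timed to the peak.

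**3. Dose effect of the reduction**

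Inputs: half-life about 10 h (Section 1.1.2), doses 7 to 10 h apart (Section 5.5), predicted mean effect 6.6 ms at 45 mg BID (Section 5.11.1). Assumptions: one compartment, rapid absorption, effect proportional to peak.

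Peak ratio QD/BID = 1/(1 + exp(−kt)), with k = ln 2/10 per hour.
- t = 7 h: ratio 0.62, so 6.6 × 0.38 = 2.5 ms.
- t = 10 h: ratio 0.67, so 6.6 × 0.33 = 2.2 ms.

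The protocol's own model has two compartments, so this is approximate. Participants with two hits may also respond more than the mean.

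**4. How many participants**

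In PRIDE-HD at 45 mg BID (81 participants), 3 had QTcF above 480 ms and 1 had a rise above 60 ms. That makes 3 to 4 with a first hit, depending on overlap.
- 120 active: 120 × 3/81 = 4.4 to 120 × 4/81 = 5.9.
- 160, if all entered the OLE: 160 × 3/81 = 5.9 to 160 × 4/81 = 7.9.
- Second hits at an assumed 25-50% recurrence: 1.1 to 3.0 of 120, and 1.5 to 4.0 of 160.

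These are probably high. PRIDE-HD counted any time point over 52 weeks of intensive ECG monitoring. OLE entry excludes QTcF above 450 ms (men) or 470 ms (women). The OLE baseline is also reset at Week 24, already on drug for active-arm completers, which makes a rise above 60 ms less likely.

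**The case against.** The best defence is that *may* here grants permission to stay on drug at QD; it does not offer a choice to keep BID. Section 5.7 is written as a series of such permissions, and its third-hit condition reads naturally as a limit on them. The OLE first-hit bullet uses the same verb for continuing drug and repeating the ECG, and nobody would call that ECG optional. The next OLE bullet presupposes the reduction. OLE footnote 8 sends the OLE Week 4 ECG to Section 4.4, where a site might apply the directive flow for Week 4 post-dose ECGs, which uses the same single ECG 1-2 hours after dosing.

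Much of this stands. For the placebo-controlled period it settles the matter, since Section 4.4 is directive there. For the OLE it makes the intended meaning likely without stating it. The directive flow is headed for the regimen's Baseline and Week 4 visits, and the OLE has its own second-hit sentence.

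A reader might infer that the OLE has no third-hit limit at all. The documents do not support that, because Section 5.7 is not confined to one period and implies such a limit. What is missing is the ECG that would detect the third hit promptly.

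**Conclusion.** The point holds as a wording gap in the OLE rule and a sentence to align in Section 5.7. It is worth correcting because it sits in the mitigation for the drug's named risk, but it is small. If *may* is taken as optional, the loss is one 3-14 day follow-up ECG and continued BID dosing, worth about 2.2 to 2.5 ms of mean predicted effect under the simple model. It would affect perhaps 1 to 4 people, on an assumed recurrence rate and counts that are probably high.

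A reader might infer that any second hit leaves a participant on BID for five or six months without an ECG. The documents do not support that. The 147-189 day interval applies to a second hit at OLE Week 4 and is mostly the ordinary schedule. A second hit at the Day 3-14 repeat ECG is followed by a scheduled ECG about 14-25 days later (7-32 with the window). The Stopping Rules apply throughout.

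The conclusion rests on the supplied text. Figure 3 and the Manual of Procedures were not available and may add detail, although Figure 3's caption covers only Baseline and Week 4.

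**What to change.** Replace the second-hit wording in the OLE flow of Section 4.4, and match Section 5.7 to it, along these lines:

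> *will be instructed to decrease to (or stay on) QD dosing, with a follow-up ECG 3-14 days later; IP must be discontinued if the Monitoring Rule is met a third time.*

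The words in brackets cover a second hit during the two-week QD start, when there is no dose to reduce. Timing the ECG from the hit and tying discontinuation to the third hit means that neither depends on a reduction having been made. Extend the heading of the OLE flow so that it also covers the OLE Week 4 and later OLE ECGs.

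Cost: one sentence in Section 5.7, one sentence and one heading in Section 4.4, and a memo to sites. Design, visit schedule, sample size and analysis are unchanged.

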5.8 Participant Compliance

Responsible study personnel will dispense the study drug. Participants will be requested to return any unused IP including empty packaging and used bottles at each study visit. Treatment compliance will be assessed at in clinic study visits through bottle counts and will be

documented and summarized by a drug-dispensing log for each participant. During phone visits, drug compliance check-in will be held to ensure participant is taking drug per dose regimen and to note any report of missed doses. Participants will be counseled on the importance of taking the IP as directed at all study visits. If poor compliance continues, (i.e., multiple missed doses resulting in less than 80% overall compliance), discontinuation of the participant from the trial should be considered and discussed with the Medical Monitor.

